**Feasibility of the Mindfulness-Based Stress Reduction Intervention for Black
Women Living with HIV Supplement**

**Principal Investigator:
[name]**

**Sponsor:
NCCIH**

National Clinical Trial (NCT) Identified Number: NCT04984681

**Version Number: v1.0
23 October 2021**

State of Compliance

The trial will be conducted in accordance with the International Conference on Harmonisation Good Clinical Practice (ICH GCP) and the applicable United States (US) Code of Federal Regulations (CFR). The Principal Investigator will monitor for deviations from or changes to the protocol that are not in accordance with approval from the Institutional Review Board (IRB), except where necessary to eliminate an immediate hazard(s) to the trial subjects. All personnel involved in the conduct of this study have completed Human Subjects Protection and ICH GCP Training.

The protocol, informed consent form(s), recruitment materials, and all subject materials will be submitted to the local Institutional Review Board (IRB) for review and approval. The protocol and the consent form must be approved before any subject is enrolled. Any amendment to the protocol will require review and approval by the IRB before the changes are implemented in the study. All changes to the consent form will be IRB approved; a determination will be made regarding whether new consent must be obtained from subjects who provided consent using a previously approved consent form.

Study Synopsis

Title:	Feasibility of the Mindfulness-Based Stress Reduction (MBSR) Intervention for Black Women Living with HIV Supplement
Study Description:	Black women living with HIV are at higher risk for experiencing stressful life events which can lead to deleterious health outcomes. MBSR offers a complementary and integrative approach for reducing stress as a mechanism for improving health outcomes. This is a randomized control pilot test aims to explore if MBSR is practical in the target population.
Objectives:	To conduct a 2-armed pilot test of the behavioral intervention compared to the standard of care to assess the feasibility and acceptability of an adapted mindfulness-based intervention for Black women living with HIV with mild cognitive impairment.
Endpoints:	Feasibility of the intervention
Study Population:	Black women living with HIV with mild cognitive impairment
Phase:	Stage I: Feasibility and pilot testing
Description of Study Intervention:	The intervention consists of the following: (1) a series of eight weekly session of 2.5 to 3 hours; (2) a silent retreat during the sixth week; (3) daily home assignments including formal and informal mindfulness practices; and (4) didactic presentations on stress and the consequences of stress.
Study Duration:	The estimated study duration of the randomized pilot study (e.g., from IRB approval to screening to finishing the study) is approximately 18 months.
Participant Duration:	The estimated participant duration (e.g., from pre-survey to post-survey) is approximately 3 months.

Schedule of Activities

Purpose

The primary purpose is to assess the feasibility of an adapted mindfulness-based intervention for Black women living with HIV with mild cognitive impairment. Please note that we are not seeking to determine the efficacy of the study. Slight deviations from the protocol are allowed with the goal of assessing efficacy in a future study.

Background

With access to effective antiretroviral therapy (ART), HIV is a manageable chronic disease. The life expectancy of people living with HIV (PLWH) is similar to that of the general population with optimal adherence to medical visits and ART¹. As a result, PLWH rarely experience HIV-associated dementia; yet, cognitive impairment is common among PLWH due to both HIV and aging². PLWH are seven times more likely to have mild cognitive impairment (MCI) than people without HIV³, which increases their risk of Alzheimer's disease and related dementias (ADRDs). Such cognitive impairment significantly impacts important daily functioning abilities, including medication adherence^{3, 4}.

Among PLWH, gender and racial disparities in cognitive impairment have been noted. Women living with HIV (WLWH) have an increased risk of poor cognitive function relative to their male counterparts living with HIV and women without HIV⁵⁻¹⁰. Further, African American (AA) WLWH are more likely to display cognitive impairment than their White female counterparts⁹. The observed differences in cognitive function are significant as the HIV epidemic disproportionately burdens AA WLWH in the US. AA WLWH account for 60% of WLWH and have mortality rates 17 times higher than rates observed for White WLWH¹¹. Increased mortality among AA WLWH is associated with suboptimal ART adherence and failure to achieve and sustain viral suppression (VS), which is notably lower in AA WLWH compared to White WLWH¹². Given the disparities noted in both poorer treatment outcomes and poorer cognitive functioning among AA WLWH, there is a critical need to develop therapeutic strategies that mitigate the cognitive impairment among AA WLWH.

Literature in the general population suggests that demographic, psychosocial, and intrapersonal factors, including socioeconomic status, age, depression, stress, and PTSD, are significantly associated with increased risk of developing cognitive impairment¹³⁻²⁰. Within PLWH, HIV biomarkers (e.g., low CD4 count, higher viral load) are also associated with poor cognitive function among WLWH^{8, 10}. Given that AA WLWH are at increased risk of both traditional cognitive impairment risk factors (e.g., stress, depression) and worse HIV severity, culturally-relevant, and gender-specific interventions to mitigate cognitive dysfunction are warranted.

There are no known cures for ADRD. Mindfulness-based stress reduction (MBSR) is a promising non-pharmacology strategy that may improve or stabilize cognition²¹⁻²³ in the general population and among specific clinical populations (e.g., female breast cancer survivors)²⁴; yet, studies among PLWH, including WLWH are lacking^{25, 26}.

Study Aim

Conduct a two-arm randomized pilot test of the adapted intervention compared to usual care among 30 Black WLWH (15/arm) to assess the feasibility of an adapted intervention.

Study Design

The study presented in this protocol is a pilot randomized controlled trial with two parallel groups and a primary endpoint of intervention feasibility. Participants will be randomized (1:1) allocation to either the control arm (usual care) or the experimental arm (MBSR).

Study Setting

Participants will be recruited from an academic ambulatory care clinic in the Southern US. The clinic provides comprehensive care to people living with HIV.

Inclusion and Exclusion Criteria

Inclusion Criteria

- 1) Cisgender females
- 2) HIV seropositive
- 3) 18 years of age or older
- 4) Able to speak English
- 5) An active patient at the study site
- 6) Have mild cognitive impairment

Exclusion Criteria

- 1) Unable to speak English
- 2) Appearing temporarily impaired (e.g., intoxicated), or
- 3) Unwilling to or legally able to provide informed consent.

Recruitment Procedures

We will use multiple methods for recruitment. Our primary method of recruitment is via a data query. Research staff will also run a data query of the outpatient HIV clinic EMR to produce a list of patients who meet the eligibility criteria. The list will be provided in the form of an Excel Spreadsheet that includes the patient's name, MRN, next scheduled clinic appointment, viral load and missed visit data for the previous 12 months, and phone number. Study staff will create a list of patients to approach at their clinic appointment to discuss the study. If the upcoming clinic appointments are not scheduled to occur soon, study staff will call potential participants using the recruitment script and ask if they are interested in participating. Once we have exhausted the list, if needed, we can then recruit using flyers or a data query. Once a potential participant calls about the study, a member of the study team will use the screening script to ask questions as well as review the potential participant's HIV clinical data (CD4 and HIV viral load). We requested a partial waiver of authorization for recruitment and screening.

Once eligible has been determined and verbal informed consent has been given. We will randomize women to either the treatment condition (MBSR; n=15) or usual care condition (usual care; n=15). Participants will receive a phone call and or text message reminder 1-2 days prior to the session. If participants are not present at the time of the session, then a member of the research team will contact the participant via phone or text message.

Study Intervention

We recruit and randomize women to either the treatment condition (MBSR; n=15) or usual care condition (usual care; n=15). Participants will be randomized to the intervention or control group using an excel-based randomization algorithm that matched conditions based on age and missed scheduled medical visits. The control group will continue to receive usual care per the HIV treatment guidelines in a team environment. The academic health center's HIV primary care clinic has implemented a team-based model of care in which physicians, nurse practitioners, nurses, social workers, counselors, and nutritionists collaborate to provide high-quality, affordable care to each patient. We decided to use usual care as the control group because previous research has demonstrated that using a matched time and attention group may have non-study effects outside of the intervention that influence outcomes ^{27, 28}. In addition, the primary goal of this study is to assess the feasibility of MBSR for Black WLWH who are currently receiving evidence-based care. Thus, MBSR will be an addition to usual care, which makes usual care a valid control condition ²⁹. MBSR sessions received by the treatment group will include an orientation, about 8-weekly sessions, and a retreat. The orientation session will be approximately 3 hours and include an overview of MBSR and mindfulness practice and discussion. Sessions 1-8 will be approximately 2.5 hours and include a brief opening meditation practice, additional meditation practices (e.g., body scan, focused awareness, yoga, etc.), group discussion, and recommendations for home practice. The retreat will be approximately 5 hours on a mutually agreed day between regularly scheduled sessions, and the activities for the retreat include group mindful eating, reviewing previously learned meditation practices, learning new practices, and group discussion. All participants will complete a pre-and post-intervention survey for feasibility purposes, not to determine efficacy or pre/post-intervention changes. This practice is not allowed by NCCIH. The intervention delivery format was changed from face-to-face to videoconferencing because of University COVID policies, and IRB approval was obtained.

Potential Risks Versus Benefits

There are minimal risks associated with this study. We will discuss stressful life events and other potentially sensitive subjects such as personal history of depression and HIV. This may cause emotional or psychological distress, and we want you to tell us if you feel distressed. We can always request a break or stop the study visit, and we can get additional help for you from a clinic social worker, psychologist, or counselor. In addition, we also ask you to perform mental tests that you may find difficult, uncomfortable, or embarrassing; however, these tests are designed to measure your peak mental abilities.

For many individuals, as they want to do their best, it is normal to feel anxious or worried about not doing well on such tests. We just ask that you do your best, but please keep in mind that no one scores perfectly on these tests.

During the group discussions, we will ask participants to refrain from using names and not discuss other participants with individuals outside the group. There is a risk that you may accidentally use your name during the session. A member of the research team will remove participants' names from the transcripts.

There are no guaranteed benefits directly to the participant. However, participants may notice improvements in awareness and increased knowledge of mindfulness.

Participant Discontinuation/Withdrawal from the Study

Participants are free to withdraw from participation in the study at any time upon request. An investigator may discontinue or withdraw a participant from the study for the following reasons:

- Significant study intervention non-compliance
- If any serious adverse event (AE) or other medical condition or situation occurs such that continued participation in the study would not be in the best interest of the participant.

Participants who complete the informed consent process and are randomized but do not receive the study intervention may be replaced. Participants who complete the informed consent process, and are randomized and receive the study intervention, and subsequently withdraw, or are withdrawn or discontinued from the study, will not be replaced.

Lost to Follow-up

A participant will be considered lost to follow-up if she fails to return for two scheduled visits and cannot be contacted by the study staff.

The following actions must be taken if a participant fails to be available for a required study visit:

- A study staff member will attempt to contact the participant to determine the reason for the missed visit, counsel the participant on the importance of attending scheduled study sessions, and ascertain if the participant wishes to and/or should continue in the study.
- Before a participant is deemed lost to follow-up, the investigator or a study staff member will make every effort to regain contact with the participant (where possible, up to 3 telephone calls).

- Should the participant continue to be unreachable, she will be considered to have withdrawn from the study with a primary reason of lost to follow-up.

Adverse Events

Adverse event means any untoward medical occurrence associated with the use of an intervention in humans, whether or not considered intervention-related (21 CFR 312.32 (a)).

An adverse event (AE) is considered “serious” if, in the view of either the investigator or sponsor, it results in any of the following outcomes:

- Death
- A life-threatening adverse event (of note, the term “life-threatening” refers to an event in which the subject was at risk of death at the time of the event, rather than to an event which hypothetically might have caused death if it were more severe)
- Inpatient hospitalization or prolongation of existing hospitalization
- A persistent or significant incapacity or substantial disruption of the ability to conduct normal life functions

There is no expectation of any adverse events or outcomes related to participation in this study. Participating in behavioral interventions such as mindfulness interventions is considered minimal risk. All participants will be given access to contact a study team member and advised to report any adverse events to the study team immediately. The study staff members will not specifically ask about adverse events during the study visit or reminder calls. Study staff members will ask participants to share voluntarily the reason for any missed research visits.

The PI or a member of the study team will record death with start dates occurring any time after informed consent is obtained until 30 days after the last day of study participation. All serious adverse events must be reported to the IRB according to regulatory requirements.

Statistical Analysis Plan

We hypothesize that the mindfulness intervention will be feasible among Black women with HIV with mild cognitive impairment.

The primary endpoint for this study is feasibility, which will be measured by the feasibility of the intervention measure³⁰, which consists of four items measured on a 5-point scale ranging from “*Completely disagree*” (1) to “*Completely agree*” (5).

Our sample size considerations are based on information obtained by previous studies in terms of sample size for pilot projects^{31, 32}, successful feasibility studies of medication adherence in HIV patients^{33, 34}, and successful feasibility studies of MBSR in populations with chronic disease^{35, 36}. Given the limited sample size and primary objective of this

application, which is to assess the feasibility and acceptability of the adapted intervention in the target population, this study is not powered sufficiently to formally detect significant group differences. We will not use our data to estimate an effect size for a future larger-scale study due to the high degree of uncertainty of estimates from small samples and where multiple measures are examined ³¹. However, we will use descriptive statistics to describe sample characteristics. Bivariate analysis will be conducted between groups using measures of effect size (e.g., Cohen's d, d-equivalent, odds ratios, etc.) and 95% confidence intervals around these measures.

Regulatory, Ethical, and Study Oversight Considerations

Consent forms describing in detail the study intervention, study procedures, and risks are given to the subject, and verbal documentation of informed consent is required prior to conducting study randomization procedures. A separate screening consent form will not be used.

Informed consent is a process that is initiated prior to the individual's agreeing to participate in the study and continues throughout the individual's study participation. Consent forms will be Institutional Review Board (IRB)-approved, and the subject will be asked to read and review the document. The investigator or a member of the research team will explain the research study to the subject and answer any questions that may arise. A verbal explanation will be provided in terms suited to the subject's comprehension of the purposes, procedures, and potential risks of the study and of their rights as research subjects. Subjects will have the opportunity to carefully review the written consent form and ask questions prior to providing verbal consent. The subjects should have the opportunity to discuss the study with their family or surrogates or think about it prior to agreeing to participate. The subject will provide verbal informed consent, which will be witnessed and documented by a member of the study team prior to any procedures being done specifically for the study. Subjects must be informed that participation is voluntary and that they may withdraw from the study at any time, without prejudice. A copy of the informed consent document will be given to the subjects for their records. The rights and welfare of the subjects will be protected by emphasizing to them that the quality of their medical care will not be adversely affected if they decline to participate in this study.

Subject confidentiality and privacy are strictly held in trust by the participating investigators and their staff. Therefore, the study protocol, documentation, data, and all other information generated will be held in strict confidence. No information concerning the study, or the data will be released to any unauthorized third party without prior written approval of the PI.

All research activities will be conducted in as private a setting as possible.

Representatives of the IRB may inspect all documents and records required to be maintained by the investigator, including but not limited to, medical records (office, clinic, or hospital) and pharmacy records for the subjects in this study. The clinical study site will permit access to such records.

The study subject's contact information will be securely stored at each clinical site for internal use during the study. At the end of the study, all records will continue to be kept in a secure location for as long a period as dictated by the reviewing IRB and/or Institutional policies.

Study subject research data, which is for purposes of statistical analysis and scientific reporting, will be stored at the UAB School of Nursing. This will not include the subject's contact or identifying information. Rather, individual subjects and their research data will be identified by a unique study identification number. The study data entry and study management systems used by research staff will be secured and password protected.

Study documents should be retained for a minimum of 3 years after the completion of the study. These documents should be retained for a longer period, however, if required by local regulations.

The independence of this study from any actual or perceived influence, such as by the pharmaceutical industry, is critical. Therefore, any actual conflict of interest of persons who have a role in the design, conduct, analysis, publication, or any aspect of this trial will be disclosed and managed. Furthermore, persons who have a perceived conflict of interest will be required to have such conflicts managed in a way that is appropriate to their participation in the design and conduct of this trial.

Bibliography

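### Staff will not specifically ask about adverse events and the only recording window names death, so capture of non-fatal events is likely incomplete and probably uneven between arms

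*Combined protocol and SAP*

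**What the plan says.** The Adverse Events section counts an event as serious if it is fatal or falls into one of three non-fatal categories: a life-threatening event, lasting or significant incapacity, or "Inpatient hospitalization or prolongation of existing hospitalization". It then makes four provisions.

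- On asking: "The study staff members will not specifically ask about adverse events during the study visit or reminder calls".
- On self-report: participants can contact a study team member and are "advised to report any adverse events to the study team immediately".
- On absences: "Study staff members will ask participants to share voluntarily the reason for any missed research visits".
- On recording and reporting: the PI or a team member "will record death with start dates occurring any time after informed consent is obtained until 30 days after the last day of study participation", and "All serious adverse events must be reported to the IRB according to regulatory requirements".

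The section's stated reason is that no related events are expected and that the intervention is of minimal risk. The Lost to Follow-up section adds a mandatory step: "The following actions must be taken if a participant fails to be available for a required study visit", the first being that "A study staff member will attempt to contact the participant to determine the reason for the missed visit".

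**The concern.** The IRB reporting duty covers all serious events, but it can operate only on events that staff know about. The same holds for the investigator's option, in the section on discontinuation, to withdraw a participant after a serious event. The visible text does not seek that knowledge for non-fatal events, and it gives no period over which they are to be recorded.

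The protocol also names a foreseeable harm: Potential Risks Versus Benefits says that the discussions may distress participants. The fallback is that participants volunteer events, and the inclusion criteria select women with mild cognitive impairment. If the remaining chances of learning of an event lie mostly in one arm, the record will be both thin and lopsided. At stake are the IRB's sight of serious events and any later statement that the intervention was well tolerated.

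**Working it through.** The documents give no adverse event rate and no capture rate, so there is no planned figure to reproduce. The check is a comparison of provisions, followed by a count of contacts.

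**Step 1. Definition, recording and reporting side by side (Adverse Events section).**

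| Event | Defined as serious | Recording instruction with a window | Goes to the IRB | Method of finding it |
|---|---|---|---|---|
| Death | yes | yes, consent to 30 days after last participation | yes | not stated |
| Life-threatening event | yes | none visible | yes | self-report or indirect |
| Hospitalization | yes | none visible | yes | self-report or indirect |
| Incapacity | yes | none visible | yes | self-report or indirect |

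Three of the four serious categories have a reporting duty but no visible recording window. The recording sentence speaks of start dates, which suits events in general better than death, so the word death may be a slip.

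**Step 2. Scheduled contacts by arm (Study Intervention section).**

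- MBSR sessions: 1 orientation + about 8 weekly sessions + 1 retreat = about 10.
- Usual care sessions: none described.
- Both arms: 2 surveys, one before and one after the intervention.
- Total: about 10 + 2 = 12 for MBSR, against 2 for usual care.

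The text does not say whether the orientation follows the first survey. Potential Risks Versus Benefits mentions cognitive tests, whose timing is not visible; they may add visits in both arms.

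**Step 3. Which indirect routes reach which arm.**

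- Distress seen in a session, with a pause or referral (Potential Risks Versus Benefits): mainly MBSR. Delivery has moved to videoconferencing, so in-person observation cannot be assumed.
- Session reminders, and contact when a participant is absent from a session (Recruitment Procedures): tied to sessions, hence mainly MBSR.
- Contact after a missed required visit (Lost to Follow-up): both arms in principle, but usual care has few visible visits to miss.
- Clinic care: all participants are active patients at the site, but no record review for adverse events is described.

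Non-fatal events that arise outside sessions and cause no absence, and most events in usual care, are left to unprompted self-report.

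**Step 4. What a clean record could show.** With complete capture, 0 events in 15 women gives an exact two-sided 95% upper limit of 1 − 0.025^(1/15) = 21.8%. If only a fraction s of affected women became known, that limit would apply to the recorded risk, and the true risk could be as high as 21.8%/s. The values of s are my assumption, shown as a range:

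| s | Upper limit on true risk |
|---|---|
| 1 | 21.8% |
| 0.75 | 29.1% |
| 0.50 | 43.6% |
| 0.25 | 87.2% |

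This shows only that the reading of zero events depends on s. It does not estimate s in either arm.

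**The case against.** The strongest reply is proportionality. This is a feasibility pilot of 30 women in a behavioral intervention. The choice not to solicit events is disclosed and reasoned, and it is paired with an open line to the study team. All serious events already go to the IRB. The Statistical Analysis Plan section sets no safety endpoint and no adverse event comparison, so uneven capture distorts no planned analysis.

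Much of this stands. It limits the consequence and keeps the severity low. It does not close the gap, because a duty to report is not a means of finding out, and the protocol's own mention of distress weakens the premise that nothing is expected.

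Three stronger readings are tempting and should not be drawn.

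- A reader might infer that staff are barred from learning of adverse events. The text says only that they will not specifically ask, at study visits and reminder calls. Self-report is invited and reasons for absence are sought.
- A reader might infer that the section contradicts itself by recording deaths alone. It does not say that only deaths are recorded, and known serious events would presumably be documented to meet the IRB duty.
- A reader might turn the contact counts into a ratio of capture between arms. The documents give no chance of disclosure per contact. Prompt self-report, or word from clinic staff, could shrink the difference.

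The Schedule of Activities could also hold a collection step that is not visible here.

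**Conclusion.** The point holds for the visible text, as a gap to reconcile. Capture of non-fatal events is likely incomplete and probably uneven between arms. The evidence for unevenness is structural (about 10 sessions against none described), and its size cannot be computed from the documents.

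Two consequences follow: non-fatal serious events may not become known for IRB reporting, and an absence of recorded events could not be read as tolerability. The primary feasibility endpoint is not shown to be affected. Severity is minor to moderate.

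The conclusion assumes that the Schedule of Activities adds no adverse event collection and no regular usual-care contact; that should be checked first.

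**What to change.** 1. Reconcile the Adverse Events section so that the definition, the recording sentence and the IRB duty cover the same events. Recording should take in all adverse events, serious or not, that become known from consent to 30 days after last participation, which is the window already in the text.
2. Replace the sentence on not specifically asking with one neutral open question about new or worsened health or emotional problems since joining. Put it to every participant in both arms at the existing post-intervention survey, and also at the missed-visit contacts already required. Keep the advice to report events at once.
3. If events are listed by arm, list all known deaths and other serious events whatever their source, so that a woman who never reaches the last survey is not lost from the listing. Show non-serious events from the common survey question separately from those found by other routes, and give the number in each arm who did not answer.

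The cost is a few minutes per participant, a simple log and an IRB amendment, with no added visits. Some unrelated minor events will be recorded, and recall over about 3 months will be imperfect in this population.

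Two limits remain. Usual-care events before the last survey will still rest mostly on self-report. No contact is described for the final 30 days, so events in that period enter the record only if they happen to become known.

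### Feasibility rests on a four-item agreement scale alone; session attendance and retention enter no planned analysis, so the evidence cannot separate a well-attended pilot from a poorly attended one if responders' ratings are similar.

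*Combined protocol and SAP*

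**What the plan says.** The Study Synopsis lists feasibility as the single endpoint and describes the purpose thus: "This is a randomized control pilot test aims to explore if MBSR is practical in the target population". The Study Aim is a comparison with usual care "among 30 Black WLWH (15/arm) to assess the feasibility of an adapted intervention".

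The Statistical Analysis Plan opens with the hypothesis: "We hypothesize that the mindfulness intervention will be feasible among Black women with HIV with mild cognitive impairment". It then names the measure: "The primary endpoint for this study is feasibility, which will be measured by the feasibility of the intervention measure", which "consists of four items measured on a 5-point scale ranging from" complete disagreement (1) to complete agreement (5). No cut-off is given. The remaining analyses are descriptive statistics for sample characteristics and between-group effect sizes with 95% confidence intervals.

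The programme is set out under Study Intervention: an orientation of about 3 hours, about eight weekly sessions of about 2.5 hours and a retreat of about 5 hours, now delivered by videoconference. The Synopsis adds "daily home assignments including formal and informal mindfulness practices".

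Staff act on attendance as the study runs. Under Recruitment Procedures they remind women before a session and contact those who are absent. Under Lost to Follow-up they apply a rule of two missed visits without contact. Under Adverse Events, "Study staff members will ask participants to share voluntarily the reason for any missed research visits". Under Participant Discontinuation/Withdrawal, a randomised woman who does not receive the intervention may be replaced, and the investigator may withdraw a woman for significant non-compliance.

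**The concern.** An agreement scale records what a woman thinks of the programme. Whether she could do it is a separate matter, and with mild cognitive impairment and a programme this long it is the main practical uncertainty. The protocol treats attendance as important in its conduct: allocation is matched on missed medical visits, absentees are contacted, and women are counselled on attending. None of that reaches the analysis.

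The replacement and withdrawal rules can widen the gap. Women for whom the programme proved impractical are the likeliest to leave the arm or not to return the survey, and no planned summary would show how many there were.

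The Purpose section looks to a future efficacy study, and the SAP declines to estimate an effect size from this sample. Attendance and retention are then among the most useful things the pilot could report, and the plan leaves them out.

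**Working it through.** **Plan's own figure.** The only design figure is 30 women, 15 per arm. It rests on earlier pilot studies. No target rate, standard deviation, dropout or precision is given, so there is nothing to reproduce.

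**Programme load** (Study Intervention): 3 + 8 × 2.5 + 5 = 28 hours over 1 + 8 + 1 = 10 contacts, before home practice.

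**Two pilots with similar ratings.** Assumed counts: 6 or 12 of 15 MBSR women reach some adequate number of sessions. The exact (Clopper-Pearson) limits for x of n are the 2.5% quantile of Beta(x, n − x + 1) and the 97.5% quantile of Beta(x + 1, n − x).

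| Women attending | Proportion | Exact 95% CI |
|---|---|---|
| 6/15 | 40% | 16.3% to 67.7% |
| 12/15 | 80% | 51.9% to 95.7% |

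If responders' mean rating is the same in both, the planned endpoint is the same in both.

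**Dependence on who responds.** Assume the 6 attenders rate the scale at a mean of 4.2.
- Only they respond: the result is 4.2.
- The other 9 respond with 2.0: (6 × 4.2 + 9 × 2.0)/15 = 43.2/15 = 2.88.
- The other 9 respond with 1.0: (6 × 4.2 + 9 × 1.0)/15 = 34.2/15 = 2.28.

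So the scale can register poor attendance, but only if non-attenders both respond and rate low. The plan secures neither.

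**Replacement.** Suppose k women randomised to MBSR never start and are replaced by women who do. The final arm shows 15/15 starting, while the true rate is 15/(15 + k).
- k = 5: 15/20 = 75%.
- k = 8: 15/23 = 65.2%.

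**What 15 women can show.** Take an illustrative rule, not in the documents: at least 11 of 15 women reach the set session count. P(pass) is the sum over j = 11 to 15 of C(15, j) p^j (1 − p)^(15 − j).

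| True rate p | 40% | 50% | 70% | 80% | 85% |
|---|---|---|---|---|---|
| P(pass) | 0.009 | 0.059 | 0.515 | 0.836 | 0.938 |

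Poor attendance (40 to 50%) and good attendance (80 to 85%) can be told apart. A true rate near 70% cannot be classified.

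**Unit of analysis.** Pooling sessions gives 15 × 10 = 150 woman-sessions. At 40% (60/150) the exact interval is 32% to 48%, against 16% to 68% with women as the unit. Sessions within a woman are not independent, so the narrower interval would be false precision.

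**Retention over both arms.** An assumed 24/30 (80%) has an exact 95% CI of 61.4% to 92.3%.

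**The case against.** A single published scale as the primary endpoint of a 30-woman pilot is a permissible choice, and nothing in the SAP forbids reporting attendance or participant flow descriptively. Both points are true, but neither brings attendance into the feasibility conclusion.

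A reader might infer that the trial would declare MBSR feasible even if most women stayed away. The documents do not support this. The scale has no cut-off, test or decision rule, so nothing formally passes. A reader might also take low attendance as expected, but nothing in the documents predicts it. The counts and scores above are scenarios, and the equal ratings in the first comparison are a condition of the argument, not a finding.

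A third inference is that all the behavioural data are already held. For attendance this is only partly fair: staff must know who is absent in order to contact her, but no attendance record kept as research data is described. For uptake it fails. The record query lists patients meeting the criteria, not women approached; its listed fields do not include cognitive impairment; women recruited by flyer may fall outside it; and no log of refusals is described.

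Finally, the Schedule of Activities is empty in the available text and the wording of the four items is not given. Attendance capture may be planned there, but that would not make it an endpoint or an analysis under the SAP as written.

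**Conclusion.** The concern holds in this limited form. The planned evidence for feasibility is one opinion scale, and it cannot distinguish a pilot that most MBSR women attended from one that most did not when responders rate similarly. In the illustration, a difference of 40 percentage points in attendance leaves no trace. The replacement and non-compliance withdrawal rules add to the problem, since women who never start can drop out of view (75% shown as 100% when 5 are replaced).

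This rests on the assumed counts and on ratings being similar among those who respond. The consequence is evidence that looks favourable, not a formal rule wrongly met. It is a cheap improvement: the scale is a legitimate measure and should stay, but on its own it does not answer whether the programme is practical.

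**What to change.** In the Statistical Analysis Plan, keep the scale and add:

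1. **Attendance per woman.** The proportion of all women randomised to MBSR who reach a session count that the investigators fix in advance. The denominator includes replaced, withdrawn and lost women, and unattended sessions count as missed. Give an exact 95% CI with women as the unit, and the mean or median number of sessions attended per woman. Do not put a binomial interval on pooled woman-sessions.
2. **Retention.** Post-survey completion out of all women randomised, by arm, with exact 95% CIs.
3. **Conclusion.** State that feasibility is judged on attendance and the scale together, against an attendance level fixed before enrolment.

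Uptake (consented out of eligible women approached) can be reported descriptively if staff log approaches and refusals. The record query alone does not supply that denominator.

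The cost is a session attendance log and SAP wording, with no added women or visits. There are two downsides. The conclusion may be less favourable than the scale alone would suggest, and precision at 15 women is limited, as the intervals above show.
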